## Clinical Protocol Synopsis

**Study Title:** A Phase II, Open Label Study of Bermekimab in Patients with Moderate to Severe Hidradenitis Suppurativa

**Sponsor:**

XBiotech USA, Inc.

**Sample Size:**

20 Subjects

**Approximate Duration:** The duration of subject participation is approximately 16 weeks, including a 3 week screening period, and a 13 week treatment period.

**Study Objectives:**

**Primary Endpoint(s):**

- Safety and Tolerability

**Secondary Endpoints:**

- Hidradenitis Suppurativa Clinical Response (HiSCR) from baseline (visit 1) to visit 13.
- Assessment of Pharmacokinetics (PK)
- Change in patient reported outcomes from baseline (visit 1) to visit 13 (VAS for disease, VAS for pain, DLQI).
- Change in Physician's Global Assessment (PGA), Disease Activity Score, and modified Sartorius score from baseline (visit 1) to visit 13.
- Change in inflammatory lesion (abscesses and inflammatory nodules) count from baseline (visit 1) to visit 13.
- Change from baseline (visit 1) to visit 13 in Hospital Anxiety Depression Scale (HADS).

**Trial Design\*****A Phase II, Open Label Study of Bermekimab in Patients with Moderate to Severe Hidradenitis Suppurativa**

- Group A (n=10): patients that have failed anti-TNF therapy will receive a total of 13 X 400mg weekly subcutaneous injections of bermekimab.
- Group B (n=10): patients that have no prior treatment with biological agents that block TNF will receive a total of 13 X 400mg weekly subcutaneous injections of bermekimab.

\*Restricted medications may be administered once during the study to alleviate acute exacerbation for HS symptoms.

**Inclusion Criteria:**

**No waivers/exemptions will be granted for protocol inclusion/exclusion criteria.**

Subjects are included in the study if they meet all of the following criteria:

- Written informed consent provided by the patient.
- Male or female, age  $\geq 18$  years.
- For group A, patients must have received and failed anti-TNF therapy. For group B, subjects must not have received any prior treatment with any anti-TNF therapy.
- Patients who have received 200mg dose of Bermekimab in this study are eligible to begin receiving 400mg dose starting with the patient's next scheduled visit for the remainder of his/her treatment plan.
- Diagnosis of HS for at least 1 year prior to screening.
- HS affecting at least two distinct anatomic areas, one of which is Hurley II or III stage.
- A total body count of abscesses and inflammatory nodules (AN) of at least 3.
- Full understanding of the procedures of the study protocol and willingness to comply with them.
- In case of female patients of childbearing potential, willingness to use one method of contraception of high efficacy during the entire study period. This method can be hormonal contraceptives or one of the following: condoms, diaphragm, or an intrauterine device. Women of non-childbearing potential include those considered to have a medical history that indicates that pregnancy is not a reasonable risk, including post-menopausal women and those with a history of hysterectomy.

**Exclusion Criteria:**

Subjects with ANY of the following will be excluded from the study:

- Age below 18 years.
- Receipt of oral antibiotic treatment for HS within 28 days prior to screening.
- Receipt of prescription topical therapies for the treatment of HS within 14 days prior to screening, and/or systemic therapies for HS (immunosuppressants, corticosteroids, retinoids, or hormonal therapies) within 28 days prior to screening.
- History of treatment with bermekimab for any reason EXCEPT patients previously treated with 200mg bermekimab dose in the previous version(s) of this study.
- History of severe allergic or anaphylactic reactions to human, humanized, chimeric, or murine monoclonal antibodies.
- Has received a live (attenuated) vaccine over the 4 weeks prior to screening.
- New intake of opioid analgesics starting within 14 days prior to screening.
- Major surgery (requiring general anesthesia or respiratory assistance) within 28 days prior to Day 0 of start of study drug.
- Hepatic dysfunction defined as any value of transaminases, of  $\gamma$ -glutamyl transpeptidase ( $\gamma$ GT) or of total bilirubin  $> 3x$  upper normal limit.
- Stage C Child-Pugh liver cirrhosis.
- History of human immunodeficiency virus (HIV) or active infection with hepatitis B virus (HBV) or hepatitis C virus (HCV).
- Neutropenia defined as  $<1,000$  neutrophils/mm^3.
- Pregnancy or lactation.

## Abbreviations

AE	Adverse event
ALT	Alanine aminotransferase (ALT, SGPT)
PT/aPTT	Prothrombin Time/Activated Partial Thromboplastin Time
ALP	Alkaline phosphate
BMI	Body mass index
BP	Blood pressure
BSA	Body Surface Area
CBC	Complete blood count
CI	Confidence interval
CH	Heavy chain constant region
CL	Light chain constant region
eCRF	Electronic Case report form
CRA	Clinical Research Associate
CRP	C-Reactive Protein
CTCAE	Common terminology criteria for adverse events
DLQI	Dermatology Life Quality Index
EC	Ethics Committee
ELISA	Enzyme-linked immunosorbent assay
GCP	Good clinical practice
GLP	Good laboratory practice
GMP	Good manufacturing practice
HADS	Hospital Anxiety Depression Scale
HbA1c	Hemoglobin A1c
HBsAg	Hepatitis B surface antigen
HiSCR	Hidradenitis Suppurativa Clinical Response Score
HIV	Human immunodeficiency virus
IFN- $\gamma$	Interferon Gamma
IGA	Investigator's Global Assessment
IgG	Immunoglobulin G
IL-1 $\alpha$	Interleukin-1 $\alpha$
IL-1 $\beta$	Interleukin-1 $\beta$
IL-1 RA	Interleukin-1 receptor antagonist
IRB	Institutional review board
PK	Pharmacokinetics
PGA	Physicians Global Assessment
pI	Isoelectric Point
SAE	Serious Adverse Event
ULN	Upper limit of normal
UV	Ultraviolet
VAS	Visual Analog Scale
WOCBP	Women of childbearing potential

## 1. BACKGROUND

### 1.1 Overview

XBiotech USA, Inc. has developed a True Human monoclonal antibody, Bermekimab, that binds the cytokine IL-1 $\alpha$  with high affinity and is an effective blocker of IL-1 $\alpha$  biological activity. IL-1 $\alpha$  is a key mediator of sterile inflammatory responses and has been implicated in the pathology of advanced cancer, cardiovascular disease, and rheumatologic disease. Clinical evidence generated to date suggests that targeting IL-1 $\alpha$  may be an effective treatment in undermining the inflammatory process that drives a wide array of diseases, including dermatologic conditions.

The active ingredient in the drug product bermekimab is MABp1, a recombinant human IgG1 monoclonal antibody specific for human interleukin-1 $\alpha$  (IL-1 $\alpha$ ). The entire bermekimab heavy and light chain sequences are identical to those found in naturally-occurring human IgG1 $\kappa$ , with the light and heavy chain variable regions being identical to those originally expressed by a peripheral blood B lymphocyte that was obtained from a healthy individual. No *in vitro* affinity maturation or modifications have been made to improve its natural binding affinity (211 +/- 31 pM). We believe that a true human antibody should be effectively non-immunogenic in humans and thus exhibit optimal activity and pharmacokinetics. XBiotech has conducted 10 clinical studies to date using the bermekimab antibody. These studies have been conducted in a wide range of therapeutic areas, from cancer to healthy volunteers, and have included several different dose levels and dosing schedules. Both intravenous and subcutaneous formulations have been explored for safety and evidence of efficacy.

Three phase 2 studies sponsored by XBiotech have been completed in dermatologic indications (acne, psoriasis and pyoderma gangrenosum), along with one investigator sponsored study in Hidradenitis Suppurativa. Subjects with moderate to severe psoriasis experienced a rapid reduction in their psoriasis area and severity index (PASI), and subjects with acne vulgaris experienced reductions of inflammatory lesion counts, as well as reduced hospital anxiety and depression scores (HADS). In both of these trials, there were few adverse events, which were all grade 1 (mild) and the only events that appeared to be related to therapy were mild injection site reactions in two patients.

The investigator initiated study enrolled patients with moderate to severe HS that were refractory to or not eligible for treatment with TNF blocking agents. The study was double blind, randomized

and placebo controlled, and utilized the Hidradenitis Suppurativa Clinical Response (HiSCR) score as a primary endpoint. Ten patients were randomized to placebo and 10 patients to treatment with bermekimab. A positive HiSCR score after 12 weeks was found in one (10%) and six (60%) patients respectively (OR: 13.50; 95%CIs: 1.19-152.61; p: 0.035). After withdrawal of therapy at week 12, a positive HiSCR score was found in nil (0%) of the placebo group and four (40%) of the treated patients after 24 weeks (p: 0.043).

Endogenous anti-IL-1 $\alpha$  antibodies are present in 5% to 28% of the general population. No negative correlations with disease have been noted for these individuals. To the contrary, the presence of natural anti-IL-1 $\alpha$  antibodies has been associated with favorable outcomes, both with respect to rheumatoid arthritis and ischemic heart disease. Animal studies also indicate that IL-1 $\alpha$  loss or antagonism does not result in harm. Moreover, the well-tolerated use of other approved biological agents that employ alternative other strategies to block IL-1 activity suggest that bermekimab's targeting of IL-1 $\alpha$  represents a safe treatment approach.

## 1.2 Rationale

Hidradenitis suppurativa (HS) is a common disorder affecting areas of the skin rich in apocrine glands. HS typically starts at adolescence. The clinical course is characterized by exacerbations and remissions of flare-ups. During these flare-ups the affected gland becomes swollen and then ruptures, with the discharge of purulent material. The duration of a flare-up is typically 3-5 days and is characterized by pain and difficulty in movement. Emotional stress is commonly associated with flare-ups, and flare-ups are commonly present in women before menses. As the disease progresses, fistulas are formed under the dermis. These fistulas often suppurate continuously. This chronic inflammation and the accompanying pain account for the fact that HS is ranked first among skin disorders in terms of adversely affecting quality of life.

HS is a common disorder. Its prevalence in Europe is 0.97% whereas in Denmark this figure is reported to be 4%. A recent review of electronic records in the United States revealed an incidence of 11.4 per 100,000 in the general population incidence. The incidence was 2.5 times higher among African Americans than among white Americans.

Based on findings showing high expression of tumor necrosis factor-alpha (TNF $\alpha$ ) in the lesions of patients, the fully humanized monoclonal anti-TNF antibody adalimumab was studied for

treatment of HS. Two large-scale randomized clinical studies (RCT) were conducted, designated PIONEER I and PIONEER II, which shared a common study design. Following an initial loading dose of 160 mg and a second 80 mg dose after two weeks, adalimumab was administered subcutaneously at a dose of 40 mg every week, and efficacy was compared to that in placebo-treated patients. The primary efficacy endpoint for both PIONEER studies was set at 12 weeks of treatment. This efficacy endpoint was the achievement of a positive hidradenitis suppurativa clinical response (HiSCR) score. After the initial 12-week treatment course, patients allocated to placebo were maintained to placebo whereas patients allocated to adalimumab were either switched to an open label extension (OLE) arm, or were further randomized to placebo, adalimumab 40 mg every other week or adalimumab 40 mg every week. Results showed that a positive HiSCR was found in 28.6% of placebo-treated patients and in 41% of adalimumab-treated patients of the PIONEER I study and in 27.6% of placebo-treated patients and in 58.9% of adalimumab-treated patients in the PIONEER II study. As stated above, after the first 12 weeks of treatment patients initially treated with adalimumab could be further randomized and received another 12 weeks of treatment with placebo, 40mg adalimumab weekly or every other week. Analysis showed that approximately half of patients showed a positive initial response to treatment, and half of these maintained this response long-term. As also stated above, after the first 12 weeks of treatment, 88 patients were switched to an OLE receiving 40 mg of adalimumab every week; positive HiSCR was achieved at weeks 120 and 168 in 56.8% and 52.3% respectively. Adalimumab has been registered in both USA and Europe for moderate to severe HS based on the results of the two PIONEER studies.

Adalimumab is an important advance for the treatment of HS. However, there remains considerable unmet need for patients with HS, including 41% to 58% of patients who have primary response failures after 12 weeks of adalimumab treatment and the 30-50% patients that have a positive initial response to treatment but relapse after 12 weeks of therapy. These primary and secondary failures to adalimumab treatment may reflect the biological heterogeneity of the HS. About half of patients, for example, over-express TNF $\alpha$  in their lesions, whereas others have lesions better characterized by the production of cytokines like interleukin (IL)-1 $\beta$  and IL-1 $\alpha$ . In a small randomized study ten patients were allocated to treatment with placebo and nine patients to treatment with anakinra (IL-1 receptor antagonist targeting both IL-1 $\beta$  and IL-1 $\alpha$ ). A positive HiSCR score was achieved in 30% and 78% of patients, respectively (p: 0.039). These results suggested that inhibition of IL-1 may be a promising treatment strategy, including that for patients evidencing primary or secondary failure of adalimumab.

[figure not shown]
An investigator initiated phase II RCT trial among patients not eligible for adalimumab (EudraCT number 2015-002321-20; ClinicalTrials.gov NCT02643654) was recently completed and showed promising results for activity of bermekimab in HS. Twenty patients with severe HS and with either primary or secondary failure of previous antiTNF agents, or who were unwilling to receive subcutaneous adalimumab treatment, were randomly allocated (1:1) to receive, in a blinded fashion, every other week treatment with placebo or bermekimab at a dose of 7.5 mg/kg IV. Treatment was administered intravenously for 12 weeks. The primary efficacy endpoint was the positive HiSCR score, that was achieved among 10% of patients allocated to placebo and 60% of patients allocated to bermekimab. The odds ratio for positive HiSCR after 12 weeks of treatment was 13.50 (95% confidence intervals 1.19-152.51, p: 0.035). Analysis of the secondary endpoints showed some remarkable advantages of bermekimab treatment versus placebo treatment: a) blind follow-up for 12 weeks after stopping treatment showed that clinical efficacy was sustained, in that a positive HiSCR score was found in 40% of the treatment group and 0% of patients receiving placebo (p: 0.043); b) positive patient reported outcomes were found at week 12 in 70% and 30% respectively (p: 0.010); c) the median time to new HS flare-up was prolonged to 11 weeks and 7 weeks respectively; d) with the use of dermal ultrasound at week 12, a 20% or more decrease in total depth of involved skin lesions was found in 77.8% and 22.2%, respectively (p: 0.029); and e) serum IL-8 was decreased at week 12 in 90% and 40% respectively (p: 0.029).

In previous dermatology studies bermekimab was well tolerated and showed impressive therapeutic activity. Dose ranging for the subcutaneous formulation of bermekimab is now being studied in a 12 week open label treatment regimen for HS in order to establish the basis for further randomized studies using subcutaneous administration.

## 2. INVESTIGATIONAL PRODUCT

### 2.1 ACTIVE INGREDIENT, PHARMACOLOGIC CLASS, STRUCTURE

The active ingredient in the drug product bermekimab is MABp1, a recombinant human IgG1 monoclonal antibody specific for human interleukin-1 $\alpha$  (IL-1 $\alpha$ ). The entire bermekimab heavy and light chain sequences are identical to those found in naturally-occurring human IgG1 $\kappa$ , with the light and heavy chain variable regions being identical to those originally expressed by a peripheral blood B lymphocyte that was obtained from a healthy individual.

**Figure 2.1: Bermekimab Antibody**

The bermekimab primary glycoform has a molecular weight of 148.1 kilodaltons. Like all IgG1 molecules, the heavy chains are joined at their hinge regions through two disulfide linkages, and each heavy chain is joined to one light chain through one disulfide linkage between their CH1 and CL domains respectively.

The main isoform has a pI of about 9.2 and comprises about 70-80% of the total isoform population in all lots that have been manufactured to date, as determined by capillary isoelectric focusing. The heavy chain CH2 domains are glycosylated primarily with the oligosaccharide structure shown in Figure 2.1, as determined by mass spectroscopy of the cleaved glycans. The glycosylated residue (Asn-302 as numbered from the N-terminus of bermekimab) has been determined by peptide mapping to be in the same highly conserved N-linked glycosylation site as found in endogenous IgG1 (Asn-297 according to the generic numbering system). Similarly, the primary glycan, commonly referred to as G0F, is the same as that found on about 22% of endogenous human IgG molecules.

The entire bermekimab heavy and light chain sequences are identical to those found in naturally-occurring human IgG1 $\kappa$ , with the light and heavy chain variable regions being identical to those originally expressed by a peripheral blood B lymphocyte that was obtained from a healthy individual.

Endogenous anti-IL-1 $\alpha$  antibody has been reported in 5% to 28% of healthy serum or plasma samples. It has been measured in cord blood, children and adults. The anti-IL-1 $\alpha$  antibodies

measured in human plasma have been strictly of the IgG class, particularly IgG1, IgG2, and IgG4. Relatively equal distribution is seen in male and female plasma. Binding affinities reported for endogenous anti-IL-1 $\alpha$  antibodies, ranging from 4 to 16 pM.

It is important to point out that affinity maturation had already taken place in the human host, and therefore no *in vitro* affinity maturation was required to increase the natural binding affinity of bermekimab. Also important is the fact that, unlike most other therapeutic IgG products, for which the Fc regions are derived from a rare human allele, XBiotech's product includes a heavy chain in which the constant (CH) region represents an allele found in approximately 70% of the human population. These two features should make for a drug product with reduced potential for immunogenicity.

## 2.2 Drug Product (Bermekimab 200 mg/ml) Description

XBiotech's dosage form is a sterile liquid formulation of 200 mg/mL bermekimab in a stabilizing isotonic subcutaneous formulation buffer at pH 6.2-6.5. The drug product is packaged in pre-filled syringes. The syringes used are OMPI EZ-Fill Nexa, 2.25mL 27G,  $\frac{1}{2}$  inch length needle, or a comparable alternative. The syringe is clear borosilicate type 1 glass containing 2mL of the formulation and is sealed using a West 1-3mL Novapure piston (plunger) with Flurotec coating. The needle is an AISI 304 stainless steel thin wall device. Drug product in syringes is stored at 5 $\pm$ 3°C and is recommended to be protected from light.

Up to 6 syringes will be packaged in each carton.

### Composition Drug Product 200mg/mL in 2 mL syringes

Ingredient	Ingredient Function	Grade	Manufacturer	Concentration	Amount per 2 mL syringe
Bermekimab Antibody	Active Substance	GMP	XBiotech USA Inc.	200 mg/mL	400 mg
Trehalose Dihydrate	Tonicity	GMP, USP/NF, EP, low endotoxin	Ferro-Pfanstiehl (USA)	60 mg/mL	120 mg
Sodium Phosphate Dibasic	pH Buffering Capacity	GMP, EP, USP	JT Baker (USA)	12 mg/mL	24 mg
Citric Acid Monohydrate	pH Buffering Capacity	GMP, EP, USP, BP, JP	Fisher (USA)	2 mg/mL	4 mg
Water for Injection	Solvent	GMP, EP, USP	Irvine Scientific (USA)	q.s.	q.s.

Phosphoric Acid	pH adjustment	GMP, EP, USP	JT Baker (USA)	pH adjustment	pH adjustment
Sodium Hydroxide,	pH adjustment	GMP, EP, USP	JT Baker (USA)	pH adjustment	pH adjustment

## 2.3 STORAGE

The recommended storage condition is at 2-8°C.

## 2.4 STABILITY

The drug product is formulated in a buffer in which most of the tonicity comes from trehalose rather than salt. Trehalose is an effective stabilizer against oxidation, aggregation, thermal, and mechanical stress. Citrate was selected as the buffering agent due to its antioxidant properties.

Extensive stability data indicates that the drug product is very stable, even under thermally and mechanically stressed conditions. Short excursions to room temperature have shown no negative effect on the product. However, the study treatment products are not to be frozen at any time. The 200 mg/ml drug product is labeled with a 12-month retest date. Every lot of 200mg/ml dosage form is also subjected to ongoing stability analysis per ICH guidelines.

## 2.5 METHOD OF ADMINISTRATION

Patients in Groups A and B will receive 400 mg administered weekly by subcutaneous injection. Each injection should be located at least one inch from previous injection sites.

**\* At least 45 minutes prior to injection, remove the pre-filled syringe from refrigeration**

***Lay the syringe on a flat surface and let it naturally warm to room temperature before injection. Do not heat the syringe.***

### Materials

Bermekimab pre-filled syringe for injection, warmed to room temperature\*

Sterile alcohol wipes

Band-aids, along with 2x2 gauze bandages and paper tape

Latex-free gloves

[figure not shown]
### Injection Site

Determine Injection site, *see illustration below:*

**Abdomen, at least 2 inches away from the belly button**, is the recommended injection site for patients with a body mass index (BMI) **below 30**. (This measurement is calculated at Screening.)

[figure not shown]
**Front Thigh or Upper Arm** is the recommended injection site for patients with a BMI of **30 or more**.

*(Note: avoid areas where the skin is burned, scarred, hardened, inflamed, swollen, or damaged).*

### Injection

- Put on gloves
- Wipe injection site clean with alcohol pads
- Raise a fold of skin between the thumb and forefinger (see illustration below).

- Insert needle as illustrated above
- Inject drug slowly
- Withdraw needle. Place band-aid over injection site if necessary (*Note: If bleeding occurs, hold pressure on the injection site for 90 seconds or until bleeding stops, and then apply gauze bandage secured by tape*).

## **2.6 AGENT ORDERING**

The Responsible Investigational Pharmacy will order study drug from XBiotech as needed.

## **2.7 POTENTIAL DRUG INTERACTIONS**

There are no known drug interactions with bermekimab. In controlled trials that combined the use of IL-1ra (anakinra) with TNF alpha inhibitors, a higher incidence of serious infection was noted. Bermekimab has not been administered concomitantly with these agents in clinical trials. However, due to potential risk, it is not recommended that bermekimab be used in combination with anti-TNF agents.

## **2.8 PROHIBITED AND RESTRICTED THERAPIES**

Treatment with certain restricted concomitant medications is allowed once during study to treat acute HS exacerbation, including:

- Systemic therapies with known effectiveness in HS, including corticosteroids, retinoids, or anti-androgen (hormonal) therapies.
- Intralesional/topical steroids
- Laser/light therapies

The use of rescue medications for worsening HS is to be reported in the electronic data capture system. A second flare up of disease and subsequent use of a second rescue therapy for any patient will result in the patient being treated as a non-responder for the purposes of data analysis.

The following concomitant therapies are *prohibited* for the entire duration of the trial:

- Biologics that target IL-1 or TNF-alpha
- Live virus vaccines
- Investigational agents other than bermekimab

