#### 4.2 EXCLUSION CRITERIA

Subjects will be excluded from the study if they meet any of the following criteria:

- Age below 18 years.
- Receipt of oral antibiotic treatment for HS within 28 days prior to screening.
- Receipt of prescription topical therapies for the treatment of HS within 14 days prior to screening, and systemic therapies for HS (immunosuppressants, corticosteroids, retinoids, or hormonal therapies) within 28 days prior to screening.
- History of treatment with bermekimab for any reason EXCEPT patients previously treated with 200mg bermekimab dose in the previous version(s) of this study.
- History of severe allergic or anaphylactic reactions to human, humanized, chimeric, or murine monoclonal antibodies.
- Administration of any live (attenuated) vaccine over the last 4 weeks.
- New intake of opioid analgesics starting within 14 days prior to screening.
- Major surgery (requiring general anesthesia or respiratory assistance) within 28 days prior to visit 1, Day 0 of start of study drug.
- Hepatic dysfunction defined as any value of transaminases, of  $\gamma$ -glutamyl transpeptidase ( $\gamma$ GT) or of total bilirubin  $> 3 \times$  upper normal limit
- Stage C Child-Pugh liver cirrhosis.
- Chronic infection by the human immunodeficiency virus (HIV), hepatitis B virus (HBV) and hepatitis C virus (HCV).
- Neutropenia defined as  $<1,000$  neutrophils/mm^3.
- Pregnancy or lactation.

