## Visit 13 (day 84 +/-2):

- ***At least 45 minutes before injection:*** Remove syringe from refrigeration and lay flat; allow to warm to room temperature. Do not heat
- Pre Injection
  - Physical Exam
  - DLQI
  - Urine pregnancy
  - HISCR
  - PGA
  - Disease Activity Score
  - Modified Sartorius
  - HADS
  - VAS for disease
  - VAS for pain
  - Blood draw for chemistry, hematology, CRP, ESR and blood draw for PK and biomarker analysis
  - Vital signs (blood pressure, pulse, oxygen saturation, respiratory rate and body temperature)
- Bermekimab subcutaneous injection, in accordance with injection site determined by BMI at Screening
- 1 hour monitoring for injection reactions
- Vital signs (blood pressure, pulse, oxygen saturation, respiratory rate and body temperature) one hour post injection (70 +/- 10 minutes)
- Adverse event monitoring
- Concomitant medications/treatments

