## 5.2 STUDY CALENDAR

Visit	Screen	1	2	3	4	5	6	7	8	9	10	11	12	13	14
Study Day		0 ± 2	7 ± 2	14 ± 2	21 ± 2	28 ± 2	35 ± 2	42 ± 2	49 ± 2	56 ± 2	63 ± 2	70 ± 2	77 ± 2	84 ± 2	91 ± 2
Informed Consent	x														
Demographics	x														
Medical/ Surgical History	x														
Infectious Disease Panel+ (part of blood draw)	x														
Serum Pregnancy (part of blood draw)	x														
Height, Weight, Body Mass Index (BMI)	x														
Vital Signs △	x	x	x	x	x	x	x	x	x	x	x	x	x	x	x
Urine Pregnancy		x	x	x	x	x	x	x	x	x	x	x	x	x	x
PK & Biomarker Blood Draw		x		x		x				x					x
Bermekimab Injection♦		x	x	x	x	x	x	x	x	x	x	x	x	x	x
DLQI		x		x		x		x		x		x		x	x
HADS		x		x		x		x		x		x		x	x
Physical Exam	x	x		x		x		x		x		x		x	x
Lab Blood Draw a,b,c	x		x		x					x				x	
HiSCR		x		x		x		x		x		x		x	x
PGA		x		x		x		x		x		x		x	x
Disease Activity Score		x		x		x		x		x		x		x	x
Modified Sartorius		x		x		x		x		x		x		x	x
VAS for disease		x		x		x		x		x		x		x	x
VAS for pain		x		x		x		x		x		x		x	x
Adverse Events		x	x	x	x	x	x	x	x	x	x	x	x	x	x
Concomitant Medications*	x	x	x	x	x	x	x	x	x	x	x	x	x	x	x

aChemistry Panel including: Albumin, Alkaline Phosphatase, ALT, AST, GGT, Bicarbonate (CO2) Calcium, Chloride, Creatinine, Glucose, Potassium, Sodium, Total Bilirubin, Total Protein, Urea Nitrogen

bHematology Panel including: Complete whole blood (WBC, HgB, Platelet, differential)

c CRP (C-Reactive Protein) and ESR (Erythrocyte Sedimentation Rate)

+ HIV antibody, Hepatitis C antibody, Hepatitis B panel (HBsAg, anti-HBc, anti-HBs), and interferon gamma release assay (IGRA)

△ Vital signs include blood pressure, pulse, oxygen saturation, respiratory rate and body temperature

♦ Each bermekimab injection will be followed by 1 hour monitoring for injection site reaction and vital signs 1 hour post injection (70+- 10 minutes)

\* Concomitant medications within 30 days before screening until 7 days after the last administration of the study drug must be recorded for the purpose of drug-drug and drug-disease interaction evaluation and signal detection.

**BMI:** Body Mass Index [BMI= weight (kg)/height (m^2)]

**DQLI:** Dermatology Quality of Life Index

**HiSCR:** Hidradenitis Suppurativa Clinical Response Score

**PGA:** Physicians' Global Assessment

**VAS:** Visual Analogue Scale

**HADS:** Hospital Anxiety Depression Scale

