### **5.3 DISCONTINUATION OF THERAPY**

If a patient is discontinued from study, the reason for discontinuation must be clearly documented in the source documentation and the EDC.

Study therapy MUST immediately be discontinued for any the following reasons:

- Withdrawal of informed consent (subject's decision to withdraw for any reason)
- Any clinical adverse event, laboratory abnormality, inter-current illness, or clinical progression of disease which, in the opinion of the Principal Investigator, indicates that continued participation in the study is not in the best interest of the subject
- Pregnancy
- Termination of the study by the sponsor
- Imprisonment or the compulsory detention for medical treatment.

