## 10.3 Analysis Sets

### 10.3.1 Safety Analysis Sets

The safety analysis set (SAF) consists of all patients that receive at least one dose of study medication and will be analyzed as treated.

The secondary endpoints will be analyzed based upon the SAF, as well as the per protocol population (PP). The per protocol population will consist of those patients that complete both the baseline (visit 1) and visit 13 assessments of their hidradenitis (HISCR, PGA, Modified Sartorius, VAS, and DLQI).

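### HiSCR can count as a bermekimab response in a patient who had HS-effective rescue therapy; a sensitivity row would show how much of the rate this accounts for

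*Combined protocol and SAP*

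**What the plan says.** The synopsis (Trial Design footnote) states: "Restricted medications may be administered once during the study to alleviate acute exacerbation for HS symptoms". Section 2.8 repeats this: "Treatment with certain restricted concomitant medications is allowed once during study to treat acute HS exacerbation, including" systemic agents that the section itself describes as effective in HS (corticosteroids, retinoids, anti-androgens), intralesional or topical steroids, and laser or light therapies. Rescue use has to be entered in the electronic data capture system. The only consequence for analysis, non-responder status, is in the sentence of 2.8 that begins "A second flare up of disease and subsequent use of a second rescue therapy for any patient will result in the patient being treated".

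The other places where a rescue rule could stand are silent on it:

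- Section 8.2 defines HiSCR from lesion counts alone: at least a 50% fall in abscesses plus inflammatory nodules, with no rise in abscesses or draining fistulas.
- Section 10.3.1 needs one dose for the safety set. For the other set, "The per protocol population will consist of those patients that complete both the baseline (visit 1) and visit 13 assessments of their hidradenitis".
- Section 10.5.3 reports the HiSCR proportion by group and pooled, with a 95% CI.
- Section 5.3 opens with "Study therapy MUST immediately be discontinued for any the following reasons" and does not list rescue use. Clinical progression is left to the investigator's opinion.

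**The concern.** The study is open label with no control group, so the HiSCR proportion stands alone as an estimate of response. If some achievers also received treatment that works in HS, the proportion mixes bermekimab's effect with that of the rescue, and nothing in the planned tables shows by how much. Section 2.8 already accepts that repeated rescue undermines a response, but it applies this only at the second flare.

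Timing sharpens the point. Eligibility (4.2) excludes "systemic therapies for HS (immunosuppressants, corticosteroids, retinoids, or hormonal therapies) within 28 days prior to screening", so baseline is protected from recent systemic treatment. No similar protection applies at the endpoint assessment, "Visit 13 (day 84 +/-2"), where a single permitted rescue may be recent. Section 1.2 says the study is meant to prepare for further randomized studies, so readers will use the reported rate for planning.

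**Working it through.** The documents state no figure to reproduce. The check is a reading of the rules, followed by arithmetic for scale.

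**Which rescue patterns lead to non-responder status?** Assume each patient meets the lesion-count criterion at visit 13.

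| Pattern before visit 13 | Second flare? | Second rescue? | Result under 2.8 |
|---|---|---|---|
| One rescue, early | no | no | achiever |
| One rescue, shortly before visit 13 | no | no | achiever |
| Several restricted therapies, same flare | no | yes, or one episode, depending on how *once* is read | achiever |
| Second flare, second rescue | yes | yes | non-responder |

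Only the last row triggers the rule. The patients in the first three rows received at least one dose and completed visits 1 and 13. If their other named assessments at those visits were also done, they are in both the safety and the per protocol sets. The two populations therefore give no contrast on rescue.

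**How recent could a rescue be?** Counting the 28-day systemic washout in 4.2 back from the nominal day of visit 13 gives 84 − 28 = day 56, which is visit 9. A systemic rescue after day 56 would be more recent than the plan accepts before screening. This is a comparison only, since the plan sets no washout before visit 13.

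**What is one patient worth?** Inputs: 10 patients per group and 20 pooled (synopsis). These are planned sizes; if fewer patients are analysed, each counts for more.

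- Shift per affected achiever in a group: 1/10 = 10 percentage points.
- Shift per affected achiever pooled: 1/20 = 5 percentage points.

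**How does that compare with the precision?** Assumptions: a starting rate of 60%, taken for illustration from the bermekimab arm of the earlier randomized trial in 1.2, and exact (Clopper-Pearson) limits, because 10.5.3 names no interval method. For x achievers out of n, the lower limit is the 0.025 quantile of Beta(x, n − x + 1) and the upper limit is the 0.975 quantile of Beta(x + 1, n − x).

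| Case | Rate | 95% CI |
|---|---|---|
| Group, 6/10 | 60% | 26.2 to 87.8% |
| Group, one reclassified, 5/10 | 50% | 18.7 to 81.3% |
| Pooled, 12/20 | 60% | 36.1 to 80.9% |
| Pooled, one reclassified, 11/20 | 55% | 31.5 to 76.9% |
| Pooled, two reclassified, 10/20 | 50% | 27.2 to 72.8% |

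Each reclassified estimate stays well inside the interval around the starting rate.

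**The case against.** The strongest reply is that 2.8 states a deliberate rule: one treated exacerbation is tolerated, and a second counts as failure. On that reading, two modalities for the same flare form one rescue episode and nothing has been overlooked. Section 1.2 puts a typical flare at 3 to 5 days, so the window for a second therapy within the same flare is short, and later treatment would often be for a new flare that 2.8 already covers. A patient who needs that much rescue may also be less likely to reach HiSCR, or may be stopped for progression under 5.3. HiSCR is secondary and descriptive, in a convenience sample. Section 10 calls itself a basis for the SAP, so its silence is weaker evidence of omission than it would be in a final plan.

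Most of this stands. A reader might infer that a second therapy for the same flare breaches the protocol and is wrongly scored as a response. The documents do not support that, because *once* can mean one administration or one treated flare. A reader might also infer that any second restricted therapy should make a patient a non-responder in the main analysis. That is a debatable preference: depending on its wording, such a rule could miss two therapies started together, or penalise a briefly interrupted single course. Nor does the eligibility washout imply one before visit 13.

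What the reply does not answer is the absence of any summary showing how far the HiSCR proportion depends on rescued patients. That holds however *once* is read, and it includes the plainly permitted single rescue.

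**Conclusion.** This is a minor point, worth a cheap improvement. The 2.8 rule is a defensible choice for the main analysis. The gap is that patients given permitted HS-effective therapy, including late systemic corticosteroid, can count as achievers in both analysis sets, and in an uncontrolled study no planned output separates them.

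The size is 10 points per affected achiever in a group and 5 points pooled, at the planned numbers. How many patients would be affected is unknown, and probably few. It would be too strong to conclude that the reported rate will be materially inflated: the documents give no rescue frequency, and a rescued achiever may be a true bermekimab responder. No formal test is affected, and the primary endpoint, safety and tolerability, does not depend on this.

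**What to change.** Keep the 2.8 rule as the main analysis and add to 10.5.3:

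*As a sensitivity summary, HiSCR (by group and pooled, with 95% CI) will also be reported with every patient who received any restricted HS therapy listed in 2.8 between visit 1 and the visit 13 assessment counted as a non-responder.*

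The difference between the main and sensitivity rates is then the share of patients counted as achievers after any rescue. It is an upper limit on what rescue could have added to the main rate.

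The cost is one table row. The data are already required: 2.8 has rescue use reported, and the study calendar (5.2) states "Concomitant medications within 30 days before screening until 7 days after the last administration of the study drug must be recorded". The downside is that the row may show a lower rate in which some true bermekimab responders count as non-responders, so it should be presented as a bound and not as a better estimate. Stating in 2.8 whether *once* means one administration or one treated flare would help sites, but is optional.
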